6.6. Dose Modification

6.6.1. Management of Increased Hypoglycemia Risk

If a hypoglycemic event occurs,

- participant should record in the study diary
 - BG level measured prior to administration of treatment, if taken
 - associated symptoms, and
 - treatment administered
- site personnel should educate and encourage participants to measure and record BG values during the symptoms of hypoglycemia in their study diaries, if safe to do so, and
- participants should be instructed to call the investigative site, as soon as possible, if they experience a hypoglycemic event that requires treatment assistance.

If a hypoglycemic event occurs, the investigator should

- use definitions and criteria provided in Section 8.3.7. to diagnose hypoglycemia
- properly categorize the suspected or confirmed event
- assess the effect and timing of the intervention(s)
- evaluate the frequency of the event
- establish the role of dietary changes in the development of the event
- establish the role of physical exercise, or any other contributing factor, in the development of the event, and

- provide participant additional education, if deemed appropriate.

Investigators are responsible for their participant's management and well-being. Therefore, it is their responsibility to implement these generally recommended measures, or to modify them, taking into account clinical and other relevant criteria.

Management of hypoglycemia in participants in tirzepatide arms

- In the absence of obvious causes (such as dietary or physical activity changes) of hypoglycemia, dose of insulin glargine (U100) should be adjusted first to manage increased risk of hypoglycemia. In case of repeated hypoglycemic events, even with a low insulin glargine (U100) dose (that is, less than 10 units/day) and despite insulin glargine (U100) dose decreases per the titration algorithm, administration of insulin glargine (U100) may be temporarily or permanently discontinued.
- Participant should be restarted on insulin glargine (U100), whenever it is safe to do so per clinical judgement of investigator.
- Metformin dose, if applicable, may also be reduced or discontinued if increased hypoglycemia risk persists, but only after appropriate adjustment of insulin glargine (U100).

Management of hypoglycemia in participants in the insulin lispro (U100) three times a day arm

- In the absence of obvious causes (such as dietary or physical activity changes) of hypoglycemia, timing of the hypoglycemic event(s) should be consulted and dose of insulin glargine (U100) and/or insulin lispro (U100) should be adjusted first to manage increased risk of hypoglycemia.
- If the participant experiences repeated hypoglycemia in spite of decreasing insulin glargine (U100) dose to a low level (less than 10 units), investigator may choose to temporarily or permanently discontinue insulin glargine (U100).
- If the participant experiences repeated hypoglycemia in spite of decreasing the relevant insulin lispro (U100) dose of the day to a low level (less than 4 units), investigator may choose to temporarily interrupt that particular dose of insulin lispro (U100). Remaining doses of insulin lispro (U100) for the day may be continued based on the clinical judgement of the investigator.
- Participant should be restarted on insulin glargine (U100) and/or regular TID regimen of insulin lispro (U100), whenever it is safe to do so per clinical judgement of investigator.
- Metformin dose, if applicable, may also be reduced or discontinued if increased hypoglycemia risk persists, but only after appropriate adjustment of insulin glargine (U100) and/or insulin lispro (U100).

6.6.2. Tirzepatide Dose Modifications

Dose modification for tirzepatide is not permitted.

6.6.3. Management of Participants with Gastrointestinal Symptoms

The tirzepatide dose escalation scheme has been designed to minimize the development of GI symptoms. During the dose escalation period, every effort should be made by the investigator to escalate and maintain participants on the corresponding tirzepatide dosage.

Dose escalation period for different doses of tirzepatide is defined as

- Weeks 0 to 8 for maintenance dose of tirzepatide 5 mg
- Weeks 0 to 16 for maintenance dose of tirzepatide 10 mg
- Weeks 0 to 24 for maintenance dose of tirzepatide 15 mg

To mitigate GI symptoms and manage participants with intolerable GI AEs during the escalation period for respective maintenance doses of tirzepatide, the investigator should follow these steps (see [Table 11](#)):

Table 11. Mitigation of Gastrointestinal Symptoms

STEP 1	Advise participants to eat smaller meals, for example, splitting 3 daily meals into 4 or more smaller meals, and to stop eating when they feel full.
STEP 2	Continue STEP 1 + Prescribe symptomatic medication, for example, anti-emetic or anti-diarrheal medication, per local country availability and individual participant needs. Use of symptomatic medication should be captured as concomitant medication in the eCRF.
STEP 3	Continue STEP 1 + STEP 2 + Temporarily interrupt tirzepatide; omit 1 dose, the participant will take 3 of 4 doses at that dose level. After the interruption, restart at the same dose with the participant taking medication to alleviate their GI symptoms. The data related to temporary interruption of study treatment should be documented in source documents and entered on the eCRF.
STEP 4	If intolerable GI symptoms or events persist despite the above measures, the investigator may decide to discontinue tirzepatide permanently. Participants who stop tirzepatide permanently will intensify insulin treatment and/or receive another glucose-lowering intervention (Section 7.1) and will continue participating in the study according to the protocol to collect all planned efficacy and safety measurements. The new glucose-lowering intervention will be recorded on the eCRF specified for collecting anti-hyperglycemic medications.

Note: De-escalation of tirzepatide will not be allowed.

Abbreviations: eCRF = electronic case report form; GI = gastrointestinal.

In the event of intolerable persistent GI symptoms that occur after the escalation period, the investigator should take the above measures to keep the participant on tirzepatide before stopping permanently and initiating another glucose-lowering agent. All dose adjustments will be managed through IWRS.

If a participant misses 3 or more consecutive doses of tirzepatide due to intolerable GI symptoms (that is, nausea, vomiting, or diarrhea) that could be reasonably attributed due to tirzepatide, despite following the mitigation steps above, tirzepatide should be discontinued. Participant will continue to titrate insulin glargine (U100) and receive another glucose-lowering intervention (if needed per clinical judgement of investigator) and will continue participating in the trial according to the protocol to collect all planned efficacy and safety measurements.

6.6.4. Insulin Lispro (U100) and Insulin Glargine (U100) Dose Modifications

After randomization, it is recommended that the insulin glargine (U100) and insulin lispro (U100) titration algorithm is followed. However, it is also important that the decision of adjustment of insulin doses is based on all available information, such as

- symptoms of hypo- and/or hyperglycemia
- previous responses to dose adjustments, and
- SMBG values other than those required as per protocol.

A reason for deviating from the insulin glargine (U100) and insulin lispro (U100) algorithm should be entered in eCRF.

6.7. Intervention after the End of the Study

The following interventional products will not be made available to participants after the conclusion of the study:

- tirzepatide, and
- insulin lispro (U100)
- insulin glargine (U100)

Participants may continue treatment with insulin glargine (U100) available locally or return to their pre-study basal insulin at investigator discretion.

7. Discontinuation of Study Intervention and Participant Discontinuation/Withdrawal

7.1 Discontinuation of Study Intervention

In rare instances, it may be necessary for a participant to permanently discontinue (definitive discontinuation) study intervention. If study intervention is definitively discontinued, the participant will remain in the study and complete all study visits and procedures.

Possible reasons leading to permanent discontinuation of investigational product

Participant decision

The participant requests to discontinue investigational product.

Discontinuation due to a hepatic event or liver test abnormality

Participants who are discontinued from investigational product due to a hepatic event or liver test abnormality should have additional hepatic safety data collected via eCRF. Discontinuation of the investigational product for abnormal liver tests **should be** considered by the investigator when a participant meets 1 of the following conditions after consultation with the Lilly designated medical monitor:

- ALT or AST >8 times ULN
- ALT or AST >5 times ULN for more than 2 weeks
- ALT or AST >3 times ULN and TBL >2 times ULN or INR >1.5
- ALT or AST >3 times ULN with the appearance of fatigue, nausea, vomiting, right upper-quadrant pain or tenderness, fever, rash, and/or eosinophilia (>5%)
- ALP >3 times ULN
- ALP >2.5 times ULN and TBL >2 times ULN
- ALP >2.5 times ULN with the appearance of fatigue, nausea, vomiting, right quadrant pain or tenderness, fever, rash, and/or eosinophilia (>5%)

Additional circumstances in which participants will be discontinued from the investigational product

A participant will be discontinued from investigational product due to any of the following:

- If a participant is inadvertently enrolled and it is determined that continued treatment with study intervention would not be medically appropriate
- Acute or chronic pancreatitis

- If a participant is diagnosed with MTC after randomization, or has postrandomization calcitonin value 35 ng/L or more that has increased at least 50% over baseline
- If a participant is diagnosed with an active or untreated malignancy (other than basal or squamous cell skin cancer, in situ carcinomas of the cervix, in situ, or grade group 1 [that is, Gleason 6 or lower] prostate cancer) after randomization
- Any significant study intervention-related hypersensitivity reaction
- Any other TEAE, SAE, or clinically significant laboratory value for which the investigator believes that permanent study intervention discontinuation is the appropriate measure to be taken
- If a participant misses 3 or more consecutive doses of tirzepatide due to intolerable GI symptoms (that is, nausea, vomiting, or diarrhea) that could be reasonably attributed to tirzepatide, despite following the mitigation steps per Section 6.6.3.
- If female participant becomes pregnant (see Section 8.3.5.)

Note: Participant will be discontinued from the study, as well.

- If a participant is diagnosed with T1DM

Note: Participant will be discontinued from the study, as well.

Participants who permanently stop tirzepatide or insulin lispro (U100) will continue to titrate insulin glargine (U100) and receive another glucose-lowering intervention, if needed per clinical judgment of investigator, and will continue participating in the trial according to the protocol to collect all planned efficacy and safety measurements.

Participants discontinuing tirzepatide or insulin lispro (U100) prematurely for any reason should complete AE and other follow-up procedures per this protocol.

See Section 1.3. for data to be collected at the time of intervention discontinuation and follow-up and for any further evaluations that need to be completed.

7.1.1. Temporary Discontinuation

In certain situations, after randomization, the investigator may need to temporarily interrupt study intervention(s). Every effort should be made by the investigator to maintain participants on study intervention(s) and to restart after any temporary interruption, as soon as it is safe to do so.

The data related to temporary interruption of study intervention(s) will be documented in source documents and entered on the eCRF.

Temporary discontinuation of tirzepatide

This shows how to manage treatment if there are missed tirzepatide doses.

Table 12. Managing Missed Tirzepatide Doses

If the number of missed tirzepatide doses is...	Then...
2 or less	treatment can be restarted at the same dose, if tirzepatide was well tolerated prior to interruption.
3 or more	the IWRS will dispense 5 mg tirzepatide irrespective of the dose the participant was receiving before the interruption and subsequently escalate as required by protocol.

Abbreviations: IWRS = interactive web-response system.

If tirzepatide interruption is due to intolerable persistent GI AE, such as nausea, vomiting, or diarrhea, the participant should be treated as suggested in Section [6.6.3](#).

Temporary discontinuation of insulin lispro (U100) three times a day

See Section [6.6.1](#). for management of increased hypoglycemia risk and temporary discontinuation of insulin lispro (U100).

7.2. Participant Discontinuation/Withdrawal from the Study

A participant may withdraw from the study

- at any time at his or her own request
- at the request of his or her designee, for example, parents or legal guardian
- at the discretion of the investigator for safety, behavioral, compliance, or administrative reasons
- if enrollment in any other clinical study involving an investigational product or enrollment in any other type of medical research judged not to be scientifically or medically compatible with this study, or
- if the participant, for any reason, requires treatment with another therapeutic agent that has been demonstrated to be effective for treatment of the study indication, discontinuation from the study occurs prior to introduction of the new agent.

A participant will be withdrawn from the study:

- if a female participant becomes pregnant
- if a participant is diagnosed with T1DM.

Discontinuation is expected to be uncommon.

At the time of discontinuing from the study, if possible, an early termination visit should be conducted, as shown in the SoA. See Section [1.3](#). for data to be collected at the time of study

discontinuation and follow-up and for any further evaluations that need to be completed. The participant will be permanently discontinued both from the study intervention and from the study at that time.

If the participant withdraws consent for disclosure of future information, the sponsor may retain and continue to use any data collected before such a withdrawal of consent. If a participant withdraws from the study, he or she may request destruction of any samples taken and not tested, and the investigator must document this in the site study records.

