6.4. Study Intervention Compliance

Participant compliance with study intervention(s) will be assessed at each visit. Compliance will be assessed by direct questioning and counting of unused study intervention(s) and/or empty cartons returned. Study intervention(s) compliance will be determined by the following:

- Study intervention(s) administration data will be recorded by the participant and reviewed by the investigator at each study visit.
- The participants will be instructed to return any unused study intervention(s) and/or empty cartons at the next visit to the study site for the purpose of performing drug accountability.

Study intervention(s) compliance for each visit interval is defined as taking at least 75% of the required injections of study intervention(s).

In addition to the assessment of a participant's compliance with study intervention(s) administration, other aspects of compliance with the study intervention(s) will be assessed at each visit based on the participant's adherence to the visit schedule, completion of study diaries, and any other parameters the investigator considers necessary.

Participants considered to be poorly compliant with their medication and/or the study procedures will receive additional training and instruction, as required, and will be reminded of the importance of complying with the protocol.

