9.4. Statistical Analyses

9.4.1. General Considerations

Statistical analysis of this study will be the responsibility of Lilly or its designee.

Any change to the data analysis methods described in the protocol will require an amendment ONLY, if it changes a principal feature of the protocol. Any other change to the data analysis methods described in the protocol, and the justification for making the change, will be described in the SAP or Clinical Study Report. Additional exploratory analyses of the data will be conducted, as deemed appropriate.

Unless otherwise noted, all tests of treatment effects will be conducted at a 2-sided alpha level of 0.05, and the CI will be calculated at 95%, 2-sided. In statistical summaries and analyses, participants will be analyzed as randomized.

There will be 2 estimands of interest in comparing efficacy of tirzepatide doses with insulin lispro (U100). The first estimand, the “efficacy” estimand, represents efficacy prior to discontinuation of study intervention without the confounding effects of antihyperglycemic rescue therapy. The second estimand, the “treatment-regimen” estimand, represents the efficacy irrespective of adherence to study intervention or initiation of rescue antidiabetic drugs.

The primary efficacy assessment, guided by the “efficacy” estimand, will be conducted using the EAS. The primary efficacy assessment, guided by the “treatment-regimen” estimand, will be conducted using the FAS. As they are intended for different purposes, no multiplicity adjustments will be made for conducting the 2 primary efficacy assessments.

Unless specified otherwise, safety assessments will be guided by an estimand comparing safety of tirzepatide (5 mg, 10 mg, and 15 mg) with insulin lispro (U100), irrespective of adherence to study intervention or initiation of antihyperglycemic rescue therapy. Thus, the safety analysis will be conducted using the SS. Selected safety analysis (for example, hypoglycemia) may be conducted excluding data after introducing another antihyperglycemic therapy.

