6.12.1.2. Primary Analysis Relative to the Treatment-Regimen Estimand

The primary analysis relative to the treatment-regimen estimand will be conducted utilizing HbA1c data in the FAS at baseline and at the 52-week visit with the aid of an analysis of covariance (ANCOVA) model. The response variable will be the primary measure and model terms will include treatment (5 mg, 10 mg, and 15 mg tirzepatide and insulin lispro), country/pooled country, and baseline metformin use (Yes/No) as fixed effects and baseline

HbA1c as a covariate. A linear contrast, averaging estimates from the individual doses, will be used to estimate the treatment effect of the combined tirzepatide arms compared with insulin lispro (U100). The ANCOVA analysis will be conducted using multiple imputation of missing primary measures (see Section 6.12.1.3 for details) and statistical inference over multiple imputation of missing data guided by Rubin (1987).

With the aid of the ANCOVA analysis, 2-sided 95% CI for mean change in HbA1c from baseline to the 52-week visit will be derived and summarized for the combined tirzepatide doses compared to insulin lispro (tirzepatide – insulin lispro). If the upper limit of the CI is $\leq 0.3\%$, then the pooled cohort of tirzepatide doses will be declared noninferior to insulin lispro (U100) relative to change in HbA1c from baseline.

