6.12.1.3. Methods for Multiple Imputations

For efficacy analyses relative to the “treatment-regimen” estimand, missing HbA1c data at the 52-week visit will be imputed based on “retrieved dropouts,” defined as patients who had their HbA1c value measured at the 52-week visit in the same treatment arm who prematurely discontinued study drug. In cases where there are not enough retrieved dropouts to provide a reliable imputation model (ie, model implemented by the SAS program does not converge), an alternative multiple imputation method with reference to the baseline data (“return to baseline” approach) will be used as the primary analysis relative to the treatment-regimen estimand. If value of imputed HbA1c change from baseline is $<-6.0\%$ or $>6.0\%$, that value will be set to -6.0% or 6.0%, respectively, to avoid unrealistic imputed values. Analyses will be conducted with multiple imputations, and statistical inference over multiple imputations will be guided by the method proposed by Rubin (1987).

Imputation of missing data using retrieved dropouts may bias towards the null which favors the noninferiority outcome. A sensitivity analysis using imputation under the non-inferiority null hypothesis will also be conducted to address this limitation (Koch 2018). In this analysis, missing data will first be imputed using retrieved dropouts from each arm. Since larger negative values represent better response for HbA1c reduction, the noninferiority margin of 0.3% will be added to the imputed values in the tirzepatide arms. This approach helps to avoid bias in the direction of making tirzepatide and insulin lispro arms more similar, therefore it reduces the chance of incorrectly demonstrating noninferiority.

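### Protocol 7.2 lets the open-label investigator end study follow-up for compliance or behavior, which can turn non-adherence into an avoidable missing Week 52 HbA1c under the treatment-regimen estimand

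*Protocol*

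**What the plan says.** **Study withdrawal.** Protocol 7.2 lists among the grounds on which a participant may leave the study: "at the discretion of the investigator for safety, behavioral, compliance, or administrative reasons". It attaches no criteria to the compliance or behavioral grounds. An early termination visit is held if possible, and 7.2 then states: "The participant will be permanently discontinued both from the study intervention and from the study at that time". The same section expects discontinuation to be uncommon.

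**Poor compliance.** Protocol 6.4 prescribes retraining: "Participants considered to be poorly compliant with their medication and/or the study procedures will receive additional training and instruction". It does not mention removal.

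**Stopping drug.** Protocol 7.1 separates stopping drug from leaving the study: "If study intervention is definitively discontinued, the participant will remain in the study and complete all study visits and procedures". Those who permanently stop tirzepatide or lispro "will continue participating in the trial according to the protocol to collect all planned efficacy and safety measurements". The two exceptions, which also end study participation, are pregnancy and a diagnosis of type 1 diabetes.

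**Estimand and analysis.** Protocol 9.4.1 says that the treatment-regimen estimand "represents the efficacy irrespective of adherence to study intervention or initiation of rescue antidiabetic drugs", and SAP 6.2 agrees. SAP 6.12.1.2 analyzes "HbA1c data in the FAS at baseline and at the 52-week visit". Under SAP 6.12.1.3, missing Week 52 values are imputed from retrieved dropouts, "defined as patients who had their HbA1c value measured at the 52-week visit in the same treatment arm who prematurely discontinued study drug". If there are too few of them for the model to converge, a return-to-baseline imputation replaces it.

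**The concern.** A participant who stops drug altogether is kept to Week 52, while one who takes it irregularly can be removed by an investigator who knows the assigned arm. The treatment-regimen estimand needs the Week 52 HbA1c of both. Removal on this ground takes away the observed value of a non-adherent participant, and also a possible donor had that participant stopped drug and stayed.

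What is at stake is the treatment-regimen analysis of the primary and key secondary objectives, which SAP 6.12 puts forward for regulatory agencies. The decision to remove can depend on arm and on how the participant is doing. The treatment burdens differ: one weekly injection with dose escalation in the tirzepatide arms, and three mealtime injections, titrated twice weekly up to Week 24, in the lispro arm.

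**Working it through.** **1. What happens to a removed participant.**
- Removal for compliance or behavior before Week 52 takes the participant off drug and out of the study (Protocol 7.2).
- The remaining contacts are an early termination visit, if possible, and a requested safety visit (Protocol 4.1.1.3). Neither is the Week 52 measurement.
- SAP 6.2 ends participation at the earliest of death, withdrawal or the safety visit, and excludes later data.
- The treatment-regimen ANCOVA uses only baseline and Week 52, so the endpoint is missing and is imputed.
- We found no passage that limits this ground or arranges for Week 52 HbA1c afterwards.

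**2. The plan's own power figures.** Inputs from Protocol 9.2: margin 0.3, SD 1.3, true difference 0, one-sided 0.025, two-sample t-test. Noncentral-t power is 80.0% for 197 versus 591 (stated 80%) and 97.7% for 591 versus 591 (stated 97%). Both are reproduced, and neither is in question.

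**3. Loss of precision.** Assume that a fraction m of every arm is removed and that imputation recovers nothing, so each n becomes n(1 − m).

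| m | Power, each dose | Power, pooled |
|---|---|---|
| 2% | 79.2% | 97.5% |
| 5% | 78.0% | 97.2% |
| 10% | 75.7% | 96.4% |
| 15% | 73.3% | 95.5% |

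**4. Shift in the between-arm difference.** Let mT and mC be the fractions removed on this ground in the pooled tirzepatide group and the lispro arm. Let D be the amount by which the removed participants' true Week 52 change is worse than the imputed one, taken as equal in both groups. Then

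shift in (tirzepatide − lispro) ≈ −(mT − mC) × D.

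- mT = 5%, mC = 2%, D = 0.5: −0.03 × 0.5 = −0.015
- mT = 5%, mC = 2%, D = 1.0: −0.030
- mT = 5%, mC = 2%, D = 1.5: −0.03 × 1.5 = −0.045
- mT = 2%, mC = 5%, same D: +0.015 to +0.045
- mT = mC: 0

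Against the margin, 0.015/0.3 = 5% and 0.045/0.3 = 15%. None of these removal rates or discrepancies is in the documents.

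**5. What that shift could mean for the primary test.** The pooled standard error is 1.3 × √(2/591) = 0.0756. Suppose the true difference sits exactly at the margin and the shift favors tirzepatide. The one-sided error then rises from 2.5% to 1 − Φ(1.960 − 0.015/0.0756) = 3.9%, or to 1 − Φ(1.960 − 0.045/0.0756) = 8.6%. A shift the other way makes the test conservative.

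**6. How far the planned sensitivity analysis reaches.** SAP 6.12.1.3 adds 0.3 to imputed tirzepatide values. For 5% of tirzepatide participants removed on this ground, that moves the difference by 0.05 × 0.3 = 0.015, the lower end of the range in step 4.

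**The case against.** **The rule is permissive.** 7.2 says that withdrawal may occur, and expects discontinuation on all grounds together to be uncommon. This stands: non-adherence can become missing data under this rule, but need not.

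**The sections can be read in sequence.** Retrain first (6.4), keep those who stop drug (7.1), withdraw as a last resort (7.2). A reader might infer that the three sections flatly contradict one another. The text does not support that, because they govern different acts. But no section states the sequence or says that withdrawal is a last resort.

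**The donors may be apt.** Once withdrawn, the participant is off drug, as the donors are. This holds for the course after removal. It does not hold for the participant who would have continued with partial adherence if kept in the study.

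**The size and direction are assumed.** This stands. A reader might infer from the unequal injection burden that removals will be unbalanced and will favor tirzepatide. The documents do not show which arm would lose more, or whether removed participants would do better or worse than the imputed values.

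**Precision is provided for.** This largely stands. The SD of 1.3% is said to allow for imputation of missing data, and pooled power stays near the stated 97% at 5% removal.

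**Mitigations exist.** The margin-based sensitivity analysis penalizes imputed tirzepatide values. Protocol 9.4.2.1 reports study discontinuation by arm with reasons, plus a Kaplan-Meier analysis, so imbalance would be visible. These help in part. The sensitivity analysis serves noninferiority in HbA1c, not the superiority or body-weight hypotheses. Reporting a loss does not recover the value.

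**Conclusion.** The point holds as an avoidable weakness in the design. Section 7.2 gives an unmasked investigator an open ground for ending follow-up of participants whose Week 52 data the treatment-regimen estimand calls for, and nothing in the protocol or SAP limits it or recovers the value.

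The effect is probably small. In the illustration the difference moves by 0.015 to 0.045, which is 5% to 15% of the margin, in a direction that cannot be determined. This rests on assumed removal of 5% versus 2%, an assumed discrepancy of 0.5 to 1.5 points, and the same discrepancy in both groups. Balanced removal with equal discrepancy cancels. The error rates in step 5 of the working apply only at the margin and only if the shift favors tirzepatide. They are not a forecast.

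The documents do not support a conclusion that the trial is underpowered, that the primary result would be biased toward tirzepatide, or that 7.1 retains every participant without exception.

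**What to change.** Reconcile Protocol 6.4, 7.1 and 7.2 so that they state together:

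- non-compliance, or behavior that does not prevent follow-up, is not by itself a ground for ending study follow-up;
- for such participants the planned visits continue, and Week 52 HbA1c and body weight are still sought unless consent is withdrawn.

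The change concerns follow-up only. The safety ground in 7.2 and all rules on stopping treatment stay as written.

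The cost is a short wording change, chiefly one bullet in 7.2, with matching statements in 6.4 and 7.1. It adds no visits, assessments or analyses. The downside is that sites go on following some participants who are hard to follow. Discretion remains where behavior makes follow-up impossible.
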